12.8 Sample size calculation

The primary effectiveness endpoint of the study is percent change of LDL-C from baseline. However, the sample size is driven by patient experience (CSQ-8) and patient activation (PAM); two key secondary outcomes in this trial. Although these outcomes are increasingly used in pragmatic and implementation trials, there is less consensus over 'clinically meaningful' differences for such outcomes. The trial has been powered to detect differences equivalent to a Cohen's effect size of 0.3, approximating a 'small-to-medium' effect in conventional terms (Cohen 1988). This would be consistent with effect sizes in pragmatic, primary care trials using self-reported health outcomes, and with similar outcomes in a recent systematic review on coaching among patients with cardiovascular risk factors (An 2020). A sample size of 300 patients per arm would be able to detect this effect size with 90% power using a one-sided significance level of 0.025 (this includes a 20% allowance for drop-out in this primary care setting).

This sample size could also detect a reduction of at least 10% change of LDL-C from baseline in the inclisiran group (+/- behavioural support) compared to the standard of care + behavioural support group (assuming a standard deviation of 30% in the control group and 20% in the inclisiran group (+/- behavioural support) based on observed results from previous inclisiran studies).

The total sample size for the study will be 900 participants.

13 Ethical considerations and administrative procedures

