#### 2.5.2 Statistical hypothesis, model, and method of analysis

The primary effectiveness objective of this study is to demonstrate superiority of each inclisiran arm compared to control in terms of the percentage change from baseline in LDL-C to Day 270 in adults with elevated LDL-C. The statistical hypotheses that will be tested for each inclisiran arm are as follows:

- $H_0$ : The difference between participants treated with inclisiran and control in the least squares mean percentage change from baseline to the Day 270 visit in LDL-C= 0
- $H_a$ : The difference between participants treated with inclisiran and control in the least squares mean percentage change from baseline to the Day 270 visit in LDL-C < 0

The primary objective will be achieved if null hypothesis  $(H_0)$  rejected at the one-sided significance level of 0.025.

The primary analysis will use an analysis of covariance (ANCOVA) model on the percent change in LDL-C from baseline to Day 270 to test the superiority of inclisiran over control after missing data imputation.

Due to probable heterogeneity of variances between treatment groups, ANCOVA model which assumes unequal variances for treatment group will be used. The model will include the fixed effects of treatment group with baseline LDL-C as a covariate.

Multiple imputation will be used to impute missing data using a washout model specified in Appendix 5.5.1. A total of 500 imputed datasets will be created. The ANCOVA model will be fitted to each imputed dataset, and results will be combined using Rubin's combination rules. The estimate and corresponding 2-sided 95% confidence intervals of mean difference between treatment groups will be calculated. p-value for hypothesis test for mean difference will also be provided. The FAS will be used for this analysis. The family-wise error rate for comparisons of the two inclisiran arms with the lipid-lowering background therapy plus behavioural support arm will be controlled using the Holm procedure.

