#### 2.6.2 Statistical hypothesis, model, and method of analysis

The key secondary variables will be analyzed as follows:

- Mean difference in total score using the validated CSQ-8 (Client Satisfaction Questionnaire) administered after treatment at day 90 between the groups will be analyzed using ANOVA. The test statistics, mean difference, 95% confidence interval and the p-value obtained using the ANOVA will be presented.
- The comparison between inclisiran and inclisiran + behavioural support also will be done and presented as mentioned above. Inclisiran arm will be considered as control for this analysis.
- The descriptive statistics for the total CSQ score will be provided for each treatment group.
- Mean difference in total score using the validated Patient Activation Measure (PAM) questionnaire administered after treatment from baseline today 90 will be analyzed using ANCOVA model. ANCOVA model which assumes unequal variances for treatment group will be used. The model will include the fixed effects of treatment group with baseline total scores as a covariate. The estimate and corresponding 2-sided 95% confidence intervals of mean difference between treatment groups will be calculated. p-value for hypothesis test for mean difference will also be provided. The FAS will be used for this analysis.
- The comparison between inclisiran and inclisiran + behavioural support also will be done and presented as mentioned above. Inclisiran arm will be considered as control for this analysis.

| Novartis | Confidential | Page 22 of 37           |
|----------|--------------|-------------------------|
| SAP      |              | Study No. CKJX839A1GB01 |

• Measures of adherence to cardiovascular disease self-management using the validated Patient Activation Measure (PAM) questionnaire administered after treatment at day 90 and using assessment of medication adherence during the study period will be summarized by providing the frequency and percentages of subjects in the four levels of the PAM scores (below) by visit and treatment. Note, highly activated patients (level 3 and level 4) are more likely to adhere to cardiovascular self-management and thus medication adherence.

Level 1: Disengaged and overwhelmed

Level 2: Become aware but still struggling

Level 3: Taking action

Level 4: Maintaining behaviors and pushinng further

• Also frequency and percentage of subjects completed each item of PAM questionnaire will be summarized by visit and treatement.

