## 3 Sample size calculation

The primary effectiveness endpoint of the study is percent change of LDL-C from baseline. However, the sample size is driven by patient experience (CSQ-8) and patient activation (PAM); two key secondary outcomes in this trial.

The trial has been powered to detect differences equivalent to a Cohen's effect size of 0.3, approximating a 'small-to-medium' effect in conventional terms

A sample size of 300 patients per arm would be able to detect this effect size with 90% power using a one-sided significance level of 0.025 (this includes a 20% allowance for drop-out in this primary care setting).

This sample size could also detect a reduction of at least 10% change of LDL-C from baseline in the inclisiran group compared to the control group (assuming a standard deviation of 30% in the control group and 20% in the inclisiran group based on observed results from previous inclisiran studies).

The total sample size for the study will be 900 participants.

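### CSQ-8 and PAM size the trial, yet their pairwise p-values have no multiplicity rule: about 21–23% chance of a nominally significant difference under the null, 12–13% in the favourable direction

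*SAP*

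**What the plan says.** - **Status of the endpoints.** Protocol 12.5.1 and SAP 2.6.1 list CSQ-8 and PAM at Day 90 among the key secondary efficacy endpoints. Protocol 12.8 says that "the sample size is driven by patient experience (CSQ-8) and patient activation (PAM); two key secondary outcomes in this trial". SAP 3 repeats this.
- **Sizing.** SAP 3 describes the trial as "powered to detect differences equivalent to a Cohen's effect size of 0.3", "with 90% power using a one-sided significance level of 0.025", with 300 per arm and a 20% drop-out allowance.
- **Tests reported.** For CSQ-8, SAP 2.6.2 says: "The test statistics, mean difference, 95% confidence interval and the p-value obtained using the ANOVA will be presented". PAM gets an ANCOVA with two-sided 95% intervals and a p-value for the mean difference. After each endpoint the SAP adds: "The comparison between inclisiran and inclisiran + behavioural support also will be done and presented as mentioned above". The secondary objective in SAP 2.6 sets inclisiran with or without support against standard of care plus support, which supplies the other two contrasts.
- **Multiplicity.** SAP 2.5.2 assigns Holm to "The family-wise error rate for comparisons of the two inclisiran arms with the lipid-lowering background therapy plus behavioural support arm". That sentence and its counterpart in Protocol 12.4.2 belong to the LDL-C analysis. Neither SAP 2.6 to 2.6.3 nor Protocol 12.5.1 gives a testing order, gate, alpha split or descriptive label for CSQ-8 or PAM.

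**The concern.** The sample size budgets the full one-sided 0.025 for a single comparison on a single endpoint, but the analysis section prints what look like six p-values.

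These endpoints carry much of the trial's new information. LDL-C superiority is very likely, given the roughly 50% reductions that Protocol 1.1.4.1 quotes. The protocol summary (Other assessments) uses Group 3 against Group 2 to ask whether supported inclisiran does better on outcomes other than LDL-C. Protocol 4.3.3.4 feeds outcomes into the choice of a preferred delivery model for the NHS. SAP 1.2 has the process evaluation explain differences between arms.

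Without a rule, a reader cannot tell which p-value, if any, supports a conclusion. A chance difference on one contrast could be explained and carried into that delivery model.

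**Working it through.** **1. Reproduce the stated sample size.** Inputs from SAP 3: d = 0.3, one-sided 0.025, 90% power, 20% drop-out.

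- n per arm = 2(1.960 + 1.282)² / 0.3² = 233.5, so 234 evaluable.
- 234 / 0.8 = 292.5, so 293 randomised, against 300 stated. This agrees.
- With 300 × 0.8 = 240 evaluable, d / √(2/240) = 3.286. Power = Φ(3.286 − 1.960) = 90.8%.

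The 90% is therefore the power of one unadjusted contrast on one endpoint.

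**2. Error rate as written.** Three equal arms with no true difference on either scale. For each endpoint there are z-tests of Group 2 v 1, Group 3 v 1 and Group 3 v 2. The documents give no CSQ-8/PAM correlation (ρ), so it is varied. Results are from 2 million simulated trials per value. Favourable means better for the inclisiran arm against Group 1, or for the supported arm in Group 3 v 2.

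| Chance of at least one | ρ = 0 | ρ = 0.3 | ρ = 0.5 |
|---|---|---|---|
| Six contrasts, two-sided p<0.05 | 22.9% | 22.4% | 21.3% |
| Four contrasts with Group 1, two-sided p<0.05 | 17.3% | 16.9% | 16.2% |
| Six contrasts, favourable at one-sided 0.025 | 12.7% | 12.2% | 11.6% |
| Four contrasts with Group 1, favourable | 8.8% | 8.5% | 8.1% |

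Hand check at ρ = 0: one endpoint with three contrasts gives 12.2% two-sided, and 1 − (1 − 0.122)² = 22.9%. In the favourable direction one endpoint gives about 6.5%, and 1 − (1 − 0.0654)² = 12.7%.

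A higher correlation lowers the figures: at ρ = 0.8 the six-contrast rates are 18.4% two-sided and 10.1% favourable.

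**3. If the CSQ-8 p-value is an overall F-test.** Suppose the CSQ-8 contrasts were read only after a significant three-group F-test, with PAM left as written. The two-sided rate over both endpoints is then 16.6% to 15.6% (ρ 0 to 0.5). With the same gate on both endpoints it is 9.8% to 9.1%. The SAP writes neither gate.

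**4. Power under a testing rule.** One contrast is tested on CSQ-8 and PAM with Holm at overall one-sided 0.025. The smaller p-value is compared with 0.0125 and, if that succeeds, the larger with 0.025. With 240 evaluable per arm:

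| Situation | Power, ρ from 0 to 0.5 |
|---|---|
| d = 0.3 on both: a given endpoint | 89–90% |
| d = 0.3 on both: at least one endpoint | 98% falling to 94% |
| d = 0.3 on both: both endpoints | 82% rising to 84% |
| d = 0.3 on one, none on the other: that endpoint | about 85% |

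For comparison, Bonferroni over all six (two-sided 0.05/6 = 0.0083) leaves 74.2% for each contrast.

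**5. Cost of gating on LDL-C.** With the SDs in Protocol 12.8 (30% and 20%), SE = √((900 + 400)/240) = 2.33 points. Power for a 10-point difference at one-sided 0.0125 is 98.0% for each inclisiran arm. It is higher still for effects near 50%.

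**The case against.** Four arguments against the point have weight.

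- **No claim is attached.** The primary objective is to demonstrate superiority and has a rejection rule. The secondary objectives are only to evaluate implementation, and nothing is concluded from a secondary p-value. This stands. It limits the consequence to uncontrolled error if the p-values are read as confirmatory. It does not remove the need for a label, because both documents call the endpoints key and size the trial on them.
- **The count of six is an inference.** SAP 2.6.2 states no alpha, sidedness or hypotheses for these tests, and only PAM has explicitly two-sided intervals. The CSQ-8 p-value could come from the overall ANOVA. The mean difference, its interval and the added inclisiran-arm comparison favour a pairwise reading but do not settle it.
- **The family may be smaller.** Group 3 against Group 2 is outside the secondary objective. The protocol summary puts it under other assessments, and the SAP adds it. On the objective's own terms there are four contrasts, which is why both counts are given.
- **Direction matters.** A reader might take 21–23% as the chance of a false win for inclisiran or for behavioural support. The documents do not support that. The figure counts differences in either direction, and at the one-sided level used for sizing the favourable rate is a little over half of it.

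**Conclusion.** The omission is real. SAP 2.6.2 gives CSQ-8 and PAM unadjusted p-values on what read as three contrasts each, while Holm is confined to LDL-C. Over six contrasts, at least one nominal two-sided p<0.05 has a chance of about 21–23%, and a false favourable result about 12–13%. Over the four contrasts with Group 1 the figures are 16–17% and 8–9%.

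These sizes rest on no true difference on either scale, equal arms, pairwise testing and an assumed correlation of 0 to 0.5. Even the smaller rates are at least three times the one-sided 2.5% used for sizing.

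A reader might infer that the trial's main conclusion is exposed. It is not: the LDL-C comparisons have their own Holm control. This is something the plan should correct, but it does not invalidate the trial.

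**What to change.** In SAP 2.6.2, before database lock:

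1. State that the CSQ-8 p-values are pairwise.
2. After both LDL-C hypotheses are rejected, test one named contrast (for example Group 3 v Group 1) on CSQ-8 and PAM, with Holm at overall one-sided 0.025. The choice of contrast is the sponsor's but must be written down.
3. Label every other CSQ-8 and PAM p-value nominal.

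If the sponsor wants no formal secondary claim, labelling all six p-values nominal closes the gap by itself.

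In Protocol 12.8 and SAP 3, say that the 90% is the power of one unadjusted contrast on one endpoint. If the Holm rule is adopted, add the figures from step 4 of the working with their assumptions. It would be wrong to quote 85% as the power for the smaller p-value, since that figure applies only when the other endpoint has no effect.

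**Cost:** wording only, with no extra participants. Protocol 12. foresees finalising the SAP before data lock, but changing 12.8 needs a written amendment under Protocol 14.1. Stated power falls slightly, and the remaining contrasts, including Group 3 v Group 2 if it is not the one named, become nominal.

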#### 2.6.3 Handling of missing values

No imputation will be applied if the scores are missing at a visit in any the questionnaire. The proportion of missing data will be included in summaries to aid interpretation.

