8.4 Efficacy Assessments

Lipid Profile

A capillary blood sample will be taken for immediate analysis of the participant's lipid profile for assessment of efficacy. This will be performed at screening/baseline visit, day 90 visit and EOS (day 270) visit (see Assessment Schedule Table 8-1).

Parameters to be assessed include:

- Non-HDL (calculated)
- LDL-C calculated using Friedewald

These data will be recorded in the eCRF

Patient Reported Outcomes Questionnaires

The Client Satisfaction Questionnaire and Patient Activation Measure (PAM) questionnaire will be administered after treatment at day 90. Patients will take the questionnaires to complete after the study visit and return them via post.

The Process Evaluation

The process evaluation will be conducted by Manchester University using the Consolidated Framework for Implementation Research (CFIR).

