#### **Post-baseline measurement:**

Post-baseline values are defined as those measurements that were collected after the first dose of study treatment or randomization visit if no study treatment has been received.

When change from baseline is of interest the following formula will be used for each scheduled visit and time-point where baseline and post-baseline values are both available:

Change from baseline = post-baseline value – baseline value.

Percent change from baseline = (change from baseline / baseline value)\*100.

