#### 2.6.1 Secondary endpoint(s)

The following are key secondary efficacy endpoints:

| Novartis | Confidential | Page 20 of 37           |
|----------|--------------|-------------------------|
| SAP      |              | Study No. CKJX839A1GB01 |

- Mean difference in total score using the validated CSQ-8 (Client Satisfaction Questionnaire) administered after treatment at day 90.
- Mean difference in total score using the validated Patient Activation Measure (PAM) questionnaire administered after treatment at day 90.
- Measures of adherence to cardiovascular disease self-management using the validated Patient Activation Measure (PAM) questionnaire administered after treatment at day 90 and using assessment of medication adherence during the study period.

All the analyses on above endpoints will be based on observed data only.

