#### 2.6.1.2 The PAM PROMs Questionnaire

This study will use the 13-point PAM questionnaire, which will be complimented by data on medication adherence to Inclisiran or standard of care recorded during the trial. The 13 item PAM consists of 13 statements relating to patients beliefs about health care, confidence in their management of health related tasks, and self-assessed knowledge of their condition.

For each statement patients are required to say how much they either agree or disagree on a response scale of 1–4, where 1 represents "strongly disagree" and 4 represents "strongly agree". Patients may also answer "non-applicable" which is scored as 0. A total score is created by summing the scores for the 13 statements and multiplying by 13/(13-n) where n is the number of statements answered as "non-applicable" or missing. The total is rounded to the nearest integer. The total score in the range [13,52] is then converted to a score in the range [0,100] using a calibration table. Note that if n>3, the calibrated score defaults to 51.

The continuous PAM scores are then categorized into four levels for descriptive purposes: according to the materials supplied by Insignia, scores less than 47.1 are level 1, scores between

47.1 and 53.2 are level 2, scores between 53.3 and 70.2 are level 3, and scores above 70.2 are level 4.

The following endpoints will be analyzed with PAM PROMs Questionnaire data.

- Endpoint: Mean difference in total score using the validated Patient Activation Measure (PAM) questionnaire administered after treatment at day 90. Summary measure: Difference between treatment groups in mean change in total scores from baseline to Day 90.
- Endpoint: Measures of adherence to cardiovascular disease self-management using the validated Patient Activation Measure (PAM) questionnaire administered after treatment at day 90 and using assessment of medication adherence during the study period. Summary measure: The frequency and percentages of subjects in the four levels of the PAM scores (below) will be summarized. Note that highly activated patients (level 3 and level 4) are more likely to adhere to cardiovascular self-management and thus medication adherence.

Level 1: Disengaged and overwhelmed

Level 2: Become aware but still struggling

Level 3: Taking action

Level 4: Maintaining behaviors and pushinng further

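### CSQ-8 and PAM, which size the trial, are analysed on observed scores only: Day 90 PAM responders without a baseline score leave the ANCOVA, and nothing tests the effect of unreturned forms

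*SAP*

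**What the plan says.** Protocol 12.8 and SAP 3 state that CSQ-8 and PAM, not LDL-C, determine the sample size: 300 per arm for a standardised difference of 0.3, with 90% power at one-sided 0.025. Of the 300, Protocol 12.8 says that "this includes a 20% allowance for drop-out in this primary care setting".

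For these endpoints SAP 2.6.1 states that "All the analyses on above endpoints will be based on observed data only", and SAP 2.6.3 adds: "No imputation will be applied if the scores are missing at a visit in any the questionnaire".

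- **CSQ-8** (SAP 2.6.2): the mean difference "between the groups will be analyzed using ANOVA". No covariate is named, and the protocol schedules no baseline CSQ-8.
- **PAM** (SAP 2.6.1.2): the summary measure is "Difference between treatment groups in mean change in total scores from baseline to Day 90". For the ANCOVA, SAP 2.6.2 says: "The model will include the fixed effects of treatment group with baseline total scores as a covariate". It names the FAS as the analysis set. SAP 2.1.1 computes changes "for each scheduled visit and time-point where baseline and post-baseline values are both available".

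On collection, Protocol 8.4 says of the Day 90 forms: "Patients will take the questionnaires to complete after the study visit and return them via post". The trial is open label. Protocol 4.5 provides two reminders at two-week intervals and contact with participants about unanswered items. SAP 2.6.3 reports the proportion missing.

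Protocol 12.5.1 leaves possible sensitivity analyses for these endpoints to the SAP. The sensitivity analyses in SAP 2.5.5 are for the primary estimand only, and none for CSQ-8 or PAM is visible in SAP 2.6 or 2.8.

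**The concern.** There are two separate problems, one for each instrument.

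**PAM.** Both the change score and the covariate need a baseline score. A Day 90 form without one cannot enter the ANCOVA, although the outcome was measured. The analysis is labelled FAS but runs on participants with two usable scores. This loses data that are already in hand.

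**CSQ-8.** The form asks how satisfied the participant was with a service that differs by arm and is not blinded. Whether a form comes back may depend on that satisfaction, and to a different degree in each arm. Groups 1 and 3 are telephoned monthly and Group 2 is not, which is one reason why return could differ. A comparison of returned forms then estimates something other than the difference in all randomised participants. The 20% allowance protects power; it does nothing about bias.

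Missing LDL-C values have a multiple-imputation model and sensitivity analyses. The two endpoints that set the size of the trial have no analysis showing whether their result survives plausible non-return.

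**Working it through.** **1. The plan's own figure.** Inputs from Protocol 12.8: d = 0.3, power 90%, one-sided alpha 0.025, drop-out 20%.

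- Evaluable per arm: 2 × (1.960 + 1.282)² / 0.3² = 233.5, so 234 (235 with the t distribution).
- After drop-out: 234 / 0.8 = 292.5, so 293. The stated 300 is a slight rounding up and is sound.
- With 300 × 0.8 = 240 evaluable, SE = √(2/240) = 0.0913 SD and power = Φ(0.3/0.0913 − 1.960) = 90.8%.

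**2. PAM: loss of responders without a baseline score.** Assumption: 240 Day 90 forms per arm, of which a share b has no baseline score. The documents give neither figure.

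| b | In the ANCOVA, 240 × (1 − b) | Power, no covariate gain |
|---|---|---|
| 5% | 228 | 89.3% |
| 10% | 216 | 87.7% |
| 15% | 204 | 85.8% |
| 20% | 192 | 83.6% |

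These powers ignore the precision gained from the baseline covariate. If baseline and Day 90 scores correlate at r, n pairs carry the information of n / (1 − r²). For the worst row, 192 / (1 − r²) = 234 gives r = √(1 − 192/234) = 0.42. At about that correlation or above, 90% power is kept.

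**3. CSQ-8: bias of the observed-only difference.** In one arm let p be the proportion not returned and g the mean of returners minus the mean of non-returners, in SD units. The mean in all participants is (1 − p) × returner mean + p × non-returner mean, so the returner mean is too high by p × g. For arms A and C the difference is therefore biased by

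p_A × g_A − p_C × g_C.

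All values of p and g below are assumptions.

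| p_A, g_A | p_C, g_C | Bias (SD) | Share of 0.3 SD |
|---|---|---|---|
| 20%, 0.25 | 20%, 0 | 0.05 | 17% |
| 20%, 0.5 | 20%, 0 | 0.10 | 33% |
| 20%, 1.0 | 20%, 0 | 0.20 | 67% |
| 20%, 0.5 | 20%, 0.5 | 0 | 0% |
| 10%, 0.5 | 30%, 0.5 | −0.10 | −33% |

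With 240 forms per arm, no true difference and a bias of +0.10 SD, the one-sided rejection rate is 1 − Φ(1.960 − 0.10/0.0913) = 19.4% instead of 2.5%. In the last row 270 and 210 forms are returned. A true difference of 0.3 SD then appears as 0.2 SD, and power is 58.5%. The bias can go either way.

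**The case against.** The strongest reply has four parts.

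1. **Safeguards exist.** Forms are chased twice, participants are contacted about unanswered items, and the proportion missing is reported. This stands, and it will reduce and describe the missingness. It does not show how far the treatment difference would move if non-returners scored differently.

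2. **The PAM loss may be harmless.** The covariate may restore power, as step 2 shows. The ANCOVA also tolerates Day 90 non-return that depends on arm and baseline score. Responders without a baseline still count in the PAM level summary, which SAP 2.6.2 gives by visit and arm. If people who return one form tend to return the other, few will lack only the baseline. All of this stands. What remains is an avoidable exclusion from the main PAM comparison.

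3. **The rates are invented.** They are assumptions, and the documents give no return rate. A reader might infer that 20% non-return is planned; the text gives a drop-out allowance, which is a different quantity. A reader might also infer that return will differ between arms because of the calls. The documents make that plausible but do not show it, and reminders are the same for all arms.

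4. **Multiple imputation would not cure CSQ-8.** A reader might conclude that imputation should become the main analysis. The documents do not support this. There is no baseline CSQ-8 and there are few strong predictors of satisfaction. The two Day 90 forms are taken home from the same visit and may often be missing together. Imputation under missing at random would leave much of the bias in step 3 in place. This objection stands, and the fix below respects it.

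**Conclusion.** The point holds as two limited gaps, and the sample size itself is correct. First, the PAM ANCOVA excludes Day 90 responders who have no baseline score. Under the assumed 5% to 20%, that is 12 to 48 of 240 per arm, with a loss of power that the covariate may wholly offset. Second, no planned analysis tests the effect of unreturned CSQ-8 or PAM forms. A moderate assumed imbalance gives a CSQ-8 bias of 0.10 SD, one third of the design effect.

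It would be too strong to say that the CSQ-8 difference is unbiased only if return is unrelated to satisfaction. The bias also vanishes if p × g is the same in both arms. The documents give no reason to expect that equality, since the services differ and are unblinded, but they do not rule it out. Equal return rates alone are not enough, because g can still differ. Nor do the documents show that the PAM comparison is underpowered.

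This concerns whole missing scores. The separate rule in SAP 2.6.1.2 for PAM forms with more than three items unanswered or not applicable is not part of it.

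**What to change.** Make two changes before database lock.

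1. **SAP 2.6.2 and 2.6.3, PAM.** Analyse the Day 90 score adjusted for baseline. Where baseline is observed, the treatment difference is identical to that from the change score with the same covariate. Fill in a missing baseline score, for example with the overall baseline mean pooled across arms or by multiple imputation of the covariate, so that every Day 90 responder is kept. Tabulate baseline return by arm. Participants are randomised at the baseline visit and complete forms away from the clinic, so baseline return could depend on arm. If it does, multiple imputation is the safer choice.

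2. **SAP 2.6.3, CSQ-8 and PAM.** Add one pre-specified delta-shift (tipping-point) sensitivity analysis for missing Day 90 scores, with shifts that vary separately by arm. Report the shifts at which the conclusion changes.

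Keep observed Day 90 outcomes as the main analysis for both instruments. The cost is a little SAP text and programming. No new data are needed, and multiple-imputation methods are already planned for LDL-C.
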